Research	
University of California, San Francisco	
Co-Principal Investigator	
de l'incipat intestigator	
thanks	
none	
none	
required

PCORNET ANALYTIC PLAN TEMPLATE

Date (mm/dd/yyyy): 05/12/2017

 Title of Project:
 Individualized Studies of Triggers of Paroxysmal Atrial Fibrillation (I-STOP-AF)

NCT03323099

Period Covered by this Report: 01/01/2017 to 04/01/2017

	0			
Principal Investigator & Institution Updated Contact Information:				
PI First Name:	[name]			
PI Last Name:	[name]			
Office [contact]			
Institution Legal Name:	University of California, San Francisco			
Address (street, city, state, zip code):	[name]			
[contact]			

Study Coordinator & Institution Updated Contact Information:			
First Name:	[name]		
Last Name:	[name]		
Office [contact]		
Institution Legal Name:	University of California, San Francisco		
Address (street, city, state, zip code):	[name]		
Telephone:			

Executive Summary

Atrial fibrillation (AF) is the most common arrhythmia and substantially reduces quality of life. The disease is often episodic, referred to as paroxysmal AF, and many patients report that certain exposures appear to trigger episodes. The effect of potential triggers on AF has never been rigorously investigated. A previous meeting between patients and investigators organically led to the formation of an AF interest group. That interest group, led primarily by AF patients, decided the most important research questions to patients would be to uncover whether AF triggers are in fact important and if involving AF patients in an "N-of-1" study of their own triggers would help improve their quality of life. We therefore designed the I-STOP-AF study, which will involve randomizing almost 500 paroxysmal AF patients to either AF episode tracking versus engaging in testing the relationship between patient-selected triggers and AF episodes utilizing a mobile-app based N-of-1 study design. Both groups will complete a validated survey to assess AF severity, essentially a measure of quality of life while living with AF, before and after the 10-week study period.

AIM 2: I-STOP- AF STUDY

1. Definitions and Roles

- **1.1. Principal Investigators:** [name], MAS will serve as the principal investigator for the I-STOP-AF study and will be responsible for all aspects of the study.
- **1.2. Site Coordinating Center:** The site will be coordinated using the Eureka platform based at the University of California, San Francisco under the supervision of [name]. [name] will serve as the Project Director.

N-of-1 Trial arm: Patients will use the Eureka mobile application and AliveCor device to execute at least one N-of-1 trial with the goal of identifying and better controlling their AF triggers. Each N-of-1 trial will last a total of 6 weeks and will include up to 3 periods of trigger exposure and 3 periods of trigger elimination with each exposure/elimination period lasting 1 week. Patients will be randomly assigned a sequence of trigger exposure and elimination periods such that they receive each treatment in each two-week block. During each N-of-1 trial, patients will track daily AF duration and severity, daily mood and sleep quality, daily AliveCor tracings and daily trigger exposure. At the end of each trial, patients will be able to review their trial results which will include visualizations of their daily AF symptom and trigger tracking over time. After completing a trial, patients will be instructed to implement any lifestyle changes they deem appropriate based on what they learned from the results of their trial. Patients will implement these changes for a period of 4 weeks during which they will continue to track AF episode duration and severity via the app. At the end of the 4-week lifestyle change period, patients will complete the Atrial Fibrillation Effect on Quality of Life survey (AFEQT) (Appendix A) and will then have the option of testing another trigger or ending their study participation.

Symptom Surveillance arm: Patients will use the Eureka app and AliveCor device to record daily AF duration and severity, daily AliveCor readings and daily mood and sleep quality for a period of 10 weeks. Patients will be able to visualize their AF, sleep and mood data in real time and will receive a weekly summary of their data via the Eureka app. At the end of the 10-week data tracking period, patients will complete the AFEQT survey and will then have the option of either ending their study participation or crossing over to the N-of-1 trial arm to test their triggers.

Primary Study Aim:

To test the comparative effectiveness of N-of-1 trials vs. data tracking alone to identify and eliminate individual level triggers and reduce AF frequency and severity as measured by the atrial fibrillation quality of life scale (AFEQT)

Secondary Aims:

- Using individual N-of-1 trials, identify modifiable exposures that increase the risk for an AF episode on an individual-level.
- By combining data from different N-of-1 trials, identify modifiable exposures that increase the risk for an AF episode on a population-level.

Exploratory Aims:

- 1. To compare exposures with respect to how much they increase risk of AF episodes
- 2. To discover factors that determine patients who respond well to N-of-1 studies
- 3. To discover modifiers of the effect of different types of AF triggers

3. Study population:

3.1 Recruitment and Enrollment:

Patients will be recruited from UCSF Cardiology and General Medicine clinics, by ancillary study teams based elsewhere, and also (primarily) on the internet. At UCSF, patients are approached by a study coordinator (or the treating MD) while they are at clinic. We also post IRB approved materials, such as brochures and posters, inviting persons in the waiting room to sign up for the study, on UCSF shuttles, and other locations. We will also use the Health eHeart Study, a national, internet-based study, as a recruitment tool.²⁰⁻²³ Potential subjects are referred to the website by friends, family and colleagues who have heard about the study, through collaborators such as StopAfib.org, a patient-led organization, or go to the mobile application because of our materials or press. The process of obtaining informed consent is especially important for patients signing up without an in-person coordinator to explain the study. We have carefully engineered this process, as described below.

- Step 1: Provide Information About the Study The majority of study patients will be approached via email. We will send a patient information about the study based on their subscription to partner organizations (stopafib.org) or the Health eHeart Study. Persons approached in the waiting room or in clinic are asked if they would be interested in participating in a research study, and given basic information about the study verbally by the study coordinator; Persons who find the mobile application read about the goals of the study, potential benefits from being in the study, who the investigators are, and which institutions are supporting the study.
- Step 2: Registration Individuals enter basic identifying information, including name, email address, phone number and date of birth, confirming no duplicates are in the study, and creation of a new study profile. Persons are then logged into the study website and able to provide electronic informed consent.
- Step 3: Review Study FAQ's--On this mobile screen the patients can review an overview of the study and frequently asked questions. This is to help set expectations for participation without the legalese required by the consent form.
- Step 4: General Informed Consent (Main Consent and Surveys) The general informed consent form is shown on the mobile application with a reminder to scroll through to the end. The Privacy and Data Security Policy receives special emphasized treatment. After reading the form, assuming they would like to continue, they indicate that they accept and would like to join the study.
- Step 5: Modular Electronic Informed Consent Patients are invited to participate in different study activity "modules" for which they are consented separately. These modules are designed and labeled clearly as to their purpose and the incremental risks and benefits. Patients for this study will be consented using a unique modular consent. Patients will be asked to consent to participation in the Aim 2 activities (described in this proposal) and will be "sheltered" from all additional HeH surveys except those integral to Aim 2 (demographics, past medical history, AF severity).

3.2 Inclusion criteria:

- Symptomatic paroxysmal AF with observed triggers
- Smartphone/tablet with data plan

3.3 Exclusion criteria:

- children (age <18 years)
- patients with plans to substantially change AF management (e.g., ablation or change in antiarrhythmic drugs) in the 6-months after enrollment; and
- non-English speakers
- Unwillingness to test AF triggers.
- Patients who have had an AV node or AV Junction ablation

3.4 Vulnerable populations:

Importantly, this research will not involve patients performing any activities or undergoing any exposures that would not normally be subjected to during the course of their normal lives. Instead, this research will primarily seek to organize those exposures in a systematic fashion. Therefore, for example, pregnant women are not necessarily excluded. However, prisoners will likely be automatically excluded as all federal and state prisons do not allow personal smartphones. As above, children will be excluded-however, atrial fibrillation in children is extremely rare.²⁴

4. Data Considerations:

4.1 Measures

Data that will be collected during the study are detailed in Table 2:

Construct	Measure(s)	Categorization	Timing	Source	
Primary Outcome (comparing N-of-1 group to data tracking group)					
Atrial fibrillation quality of life	AFEQT score	Integer (20-140). Survey includes 20 questions 1-7	Baseline and 10 weeks	Eureka app	
		score for each			
Primary Outcomes	(for individual-level	N-of-1 trials within th	e N-of-1 group)	Γ	
Atrial fibrillation	ECG flagged by	1=Yes	Daily and whenever	AliveCor app	
device	algorithm	U=INO	a symptomatic		
Atrial fibrillation	Patient report	1=Yes 0=No	Daily	Eureka app	
Atrial fibrillation duration	Patient report (hrs and minutes)	Integer 0-60 hrs, 0-60 min	Daily (queried only if self-reported atrial fibrillation=Yes on that day)	Eureka app	
Atrial fibrillation severity	Patient report	Integer 1-7, ordinal scale 1=least severe	Daily (queried only if self-reported atrial fibrillation=Yes on that day)	Eureka app	
SECONDARY ENDPOINTS					
AliveCor confirmed atrial fibrillation event	Patient reported atrial fibrillation event confirmed	1=Yes 0=No	Daily and whenever a symptomatic episode occurs	AliveCor app and Eureka app	

Table 2

within the N-of-1 group and compared to data tracking in last	by report from AliveCor device			
Count of AF Frequency	The number of patients reported AF episodes during the final month of enrollment	Integer 0-7—count	Daily	Eureka app
Total duration of AF episodes	Total duration of patient reported AF episodes daily during the final month of enrollment	Continuous 0-60 min, 0-24 hours 0= no answer	Daily (only if self-reported atrial fibrillation=Yes on that day)	Eureka app
Average severity of AF episodes	average severity of patient reported AF episodes daily during final month of enrollment	Continuous (range 1-7 using, Ordinal Scale 1=least severe 0= no answer	Daily (only if self-reported atrial fibrillation=Yes on that day)	Eureka app
Safety Measures Emergency room visit	Patient report	1=Yes 2=No 3=Don't know If yes, date and hospital location	Monthly: Reported at 4 & 8 weeks; actual emergency room visits will be categorized by day	Eureka app
Emergency room visit related to atrial fibrillation	Patient report	1=Yes 2=No 3=Don't know	Monthly (queried only if emergency room visit=Yes for that month) Reported at 4 &8 weeks.	Eureka app
Hospitalization	Patient report	1=Yes 2=No 3=Don't know If yes, date and hospital location	Monthly; actual hospitalizations will be categorized by day reported at 4 and 8 weeks.	Eureka app
Hospitalization related to atrial fibrillation	Patient report	1=Yes 2=No 3=Don't know	Monthly (queried only if hospitalization=Yes for that month)	Eureka app

			Reported at 4 &8	
			weeks.	
Cerebrovascular accident	Patient report	1=Yes 2=No 3=Don't know If yes, date and location diagnosis	Monthly; reported at 4 &8 weeks.	Eureka app
Myocardial infarction	Patient report	made 1=Yes 2=No 3=Don't know If yes, date and location diagnosis made	Monthly; reported at 4 &8 weeks.	Eureka app
Heart failure	Patient report	1=Yes 2=No 3=Don't know If yes, date and location diagnosis made	Monthly; reported at 4 &8 weeks.	Eureka app
MODIFIERS	_			
Age	Patient report	Continuous	Baseline only	Eureka app
Gender Identity	Patient report	1=Woman 2=Man 3=Transgender Woman 4=Transgender Man 5=Genderqueer 6=Another gender identity 7=Decline to state	Baseline only	Eureka app
Sex	Patient report	1=Male 2=Female 3=Prefer not to state	Baseline only	Eureka app
Race	Patient report	1=Black 2=White 3=Asian 4=Native Hawaiian or Pacific Islander 5=American Indian or Alaska Native 6=Some other race 7=Don't know	Baseline only	Eureka app

		8=Prefer not to		
		state		
Hispanic	Patient report	1=Not Hispanic 2=Yes: Mexican, Mexican American or Chicano 3=Yes: Puerto Rican 4=Yes: Cuban 5=Yes: Cuban 5=Yes: Mixed Hispanic, Latino or Spanish Origin 6=Yes: Other Hispanic, Latino, or Spanish Origin 7=Don't know 8=Prefer not to state	Baseline Only	Eureka app
Education level	Patient report	1=No formal schooling 2=Some school, but did not graduate high school 3=High school diploma or equivalent 4=Associate degree 5=Some college 6=Bachelor's degree 7=Master's degree 8=Doctorate 9=Professional doctorate 10=Other 11=Don't know 12=Prefer not to state	Baseline Only	Eureka app
Household income	Patient report	1= Under \$10,000 2= \$10,000 to under \$20,000 3= \$20,000 to under \$30,000	Baseline Only	Eureka App

		4=\$30,000 to		
		under \$40,000		
		5= \$40,000 to		
		under \$50,000		
		6= \$50,000 to		
		under \$75,000		
		7= \$75,000 to		
		under \$100,000		
		8= \$100,000 to		
		under \$150,000		
		9= More than		
		\$150,000		
		10= Don't know		
		11= Prefer not to		
		state		
Household size	Patient report	Integer 0-20	Baseline Only	Eureka app
Hoight	Dationt report	Integer 1 10 ft	Pacolino Only	Euroka ann
Height		0 11 inchos	Baseline Only	Eureka app
		0-11 menes		
Weight (pounds)	Patient report	Integer 1-999	Baseline Only	Eureka app
Hypertension	Patient report	1=Yes	Baseline Only	Eureka app
		2=No		
		3=Don't Know		
Diabetes	Patient report	1=Yes	Baseline Only	Eureka app
		2=No		
		3=Don't know		
Coronary artery	Patient report	1=Yes	Baseline Only	Eureka app
disease		2=No		
		3=Don't know		
Heart Attack	Patient report	1=Yes	Baseline Only	Eureka app
		2=No		
		3=Don't know		
Peripheral Artery	Patient report	1=Yes	Baseline Only	Eureka app
Disease		2=No		
		3=Don't know		
Congestive Heart	Patient report	1=Yes	Baseline Only	Eureka app
Failure		2=No		
		3=Don't know		
Stroke	Patient report	1=Yes	Baseline Only	Eureka app
		2=No		
		3=Don't know		
Heart murmur	Patient report	1=Yes	Baseline Only	Eureka app
		2=No		
		3=Don't know		

Sleep Apnea	Patient report	1=Yes	Baseline Only	Eureka app
		2=No		
		3=Don't know		
First degree family	Patient report	1=Yes	Baseline Only	Eureka app
member with		2=No		
atrial fibrillation		3=Don't know		
Currently on	Patient report	1=Flecainide	Baseline Only	Eureka app
antiarrhythmic		2=Propafenone		
drugs		3=Aminodarone		
		4=Dronedarone		
		5=Sotalol		
		6=Dofetilide		
		7=None of the		
		above		
Currently take	Patient report	1= Wafarin	Baseline Only	Eureka app
antiplatelets and		2=Aspirin		
anticoagulants		3=Dabigatran		
		4=Rivaroxaban		
		5=Apixaban		
		6 =Edoxaban		
		7=Clopidogrel		
		8=Prasugrel		
		9=None of the		
		above		
Sleep	Patient report	1=Amazing	Daily	Eureka app
		2=Good		
		3=Average		
		4=Bad		
		5=Horrible		
Mood	Patient report	1=Neutral	Daily	Eureka app
		2=Happy		
		3=Depressed		
		4=Angry		
		5=Anxious		
		6=Stressed		

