1.5 Study Procedures

Randomization/Baseline evaluation: Potential participants will be identified via the Health eHeart Study and the StopAfib.org patient advocacy organization and reached out to via email campaigns. Of note, invitations will be extended broadly to include friends family and acquaintances of those participants. Patients may also be recruited directly from UCSF clinics or other web-based sources of potentially interested atrial fibrillation patients. The study email campaign will contain an overview of the study. If the patient is interested in participating in the study there will be a link for the participant that will take them to the mobile app store to

download the Eureka app. Potential participants will be prompted to register an account and will complete an inclusion/ exclusion criteria survey within the Eureka app. If eligible, they will continue on to the study consent form (Appendix B). Upon completion of the electronic study consent, Eureka will randomize participants to either the N-of-1 or the symptom surveillance arm of the study with a 1:1 allocation ratio.

Participants will then be asked to complete baseline data collection which will include basic demographics, medical history, and current atrial fibrillation medications. After baseline data collection, the study team will ship AliveCor devices to study participants over a period of two weeks. At the end of this two week period, participant will be prompted to visit the Eureka application to complete a device consent and then will be instructed to download the AliveCor app and link their AliveCor device to their Eureka account. All participants will then complete the Atrial Fibrillation Effect on QualiTy of Life survey (AFEQT) (Appendix A). Once they complete the survey, the app will show participants which study arm they have been randomized to and prompt them to begin the appropriate study activities.

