1.5.1 Outcome Measures

The primary study outcome is change in quality of life, measured by the AFEQT, between those randomized to N-of-1 experiments versus those that tracking their data alone. Secondary outcomes will include results of individual-level N-of-1 trials.

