Please choose one number which best describes your situation. treatment descriptive none not applicable Worrying about the treatment side effects from medications side_effects radio none required Worrying about complications or side effects from	 2, 2 - Hardly bothered 3, 3 - A little bothered 4, 4 - Moderately bothered 5, 5 - Quite a bit bothered 6, 6 - Very bothered 7, 7 - Extremely bothered 1, 1 - Not at all bothered
Please choose one number which best describes your situation. treatment descriptive none not applicable Worrying about the treatment side effects from medications side_effects radio none required Worrying about complications or side effects from procedures like catheter ablation, surgery, or	 2, 2 - Hardly bothered 3, 3 - A little bothered 4, 4 - Moderately bothered 5, 5 - Quite a bit bothered 6, 6 - Very bothered 7, 7 - Extremely bothered 1, 1 - Not at all bothered 2, 2 - Hardly bothered
Please choose one number which best describes your situation. treatment descriptive none not applicable Worrying about the treatment side effects from medications side_effects radio none required Worrying about complications or side effects from	 2, 2 - Hardly bothered 3, 3 - A little bothered 4, 4 - Moderately bothered 5, 5 - Quite a bit bothered 6, 6 - Very bothered 7, 7 - Extremely bothered 1, 1 - Not at all bothered 2, 2 - Hardly bothered 3, 3 - A little bothered
Please choose one number which best describes your situation. treatment descriptive none not applicable Worrying about the treatment side effects from medications side_effects radio none required Worrying about complications or side effects from procedures like catheter ablation, surgery, or	 2, 2 - Hardly bothered 3, 3 - A little bothered 4, 4 - Moderately bothered 5, 5 - Quite a bit bothered 6, 6 - Very bothered 7, 7 - Extremely bothered 1, 1 - Not at all bothered 2, 2 - Hardly bothered

radio	6, 6 – Very bothered
none	7, 7 – Extremely bothered
required	
Worrying about side effects of blood thinners such	1, 1 – Not at all bothered
as nosebleeds, bleeding gums when brushing	2, 2 – Hardly bothered
teeth, heavy bleeding from cuts, or bruising.	3, 3 – A little bothered
	4, 4 – Moderately bothered
blood_thinners	5, 5 – Quite a bit bothered
radio	6, 6 – Very bothered
none	7, 7 – Extremely bothered
required	
Worrying or feeling anxious that your treatment	1, 1 – Not at all bothered
interferes with your daily activities	2, 2 – Hardly bothered
	3, 3 – A little bothered

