daily_activities	4, 4 – Moderately bothered
radio	5, 5 – Quite a bit bothered
none	6, 6 – Very bothered
required	7, 7 – Extremely bothered
On a scale of 1 to 7, overall, how satisfied are you at the present time with:	Not a question
Please choose one number which best describes your situation.	
overall_satisfaction descriptive none not applicable	
How well your current treatment controls your	1, 1 – Extremely satisfied
How well your current treatment controls your atrial fibrillation?	2, 2 – Very satisfied
	3, 3 – Somewhat satisfied
treatment control	4, 4 – Mixed with satisfied and dissatisfied
treatment_control radio	5, 5 – Somewhat dissatisfied
radio	
none required	6, 6 – Very dissatisfied
requirea	7, 7 – Extremely dissatisfied
The extent to which treatment has relieved your	1, 1 – Extremely satisfied
symptoms of atrial fibrillation?	2, 2 – Very satisfied
	3, 3 – Somewhat satisfied
treatment_relieved	4, 4 – Mixed with satisfied and dissatisfied
radio	5, 5 – Somewhat dissatisfied
none	6, 6 – Very dissatisfied
required	7, 7 – Extremely dissatisfied
-	.,. Intromoty abbattoried

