4.2. Primary Endpoints

- 1. **Atrial fibrillation quality of life** will be measured by the AFEQT survey monthly and will be used in comparing of the N-of-1 arm to the tracking arm. The primary outcome will be change from baseline (randomization) to 10 weeks.
- 2. **Self-reported atrial fibrillation event** Each day patients will report if they have had an atrial fibrillation event.
- 3. Atrial fibrillation duration Each day patients will report the total amount of time during which they had atrial fibrillation adding up time over all events over the day. For days on which no event occurred, the time will be zero.

4. **Atrial fibrillation severity** Each day patients will record the severity of their atrial fibrillation on a scale of 1-7 with a score of 1 given if no event occurred.

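### The SAP's 20-item primary AFEQT total includes two treatment-satisfaction items, whose meaning may differ by arm at week 10 in this open trial

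*SAP*

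**What the plan says.** Protocol 1.5.1 sets the endpoint: "The primary study outcome is change in quality of life, measured by the AFEQT". SAP 4.2 names atrial fibrillation quality of life as the first primary endpoint, which "will be measured by the AFEQT survey monthly and will be used in comparing of the N-of-1 arm to the tracking arm". The only description of the score is the entry in SAP 4.1, Table 2: "Integer (20-140). Survey includes 20 questions 1-7". Neither SAP 4.2 nor SAP 5.4.1 gives a scoring algorithm, and no section scores any item separately.

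In Protocol Appendix A the first 18 scored items carry a four-week recall stem. The last of them begins "Worrying or feeling anxious that your treatment". The stem then changes to "On a scale of 1 to 7, overall, how satisfied are you at the present time with", followed by two items: "How well your current treatment controls your atrial fibrillation" and "The extent to which treatment has relieved your" symptoms.

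Protocol 1.5 has participants complete the baseline AFEQT, after which "the app will show participants which study arm they have been randomized to". SAP 5.4.1 compares the arms by analysis of covariance of the 10-week score on the baseline score.

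**The concern.** A score labelled quality of life includes two items that ask something else, over a different time frame. Both are ratings of treatment, and what participants count as treatment may come to differ between the arms during the trial. The N-of-1 arm chooses and tests a trigger, sees its own results and then has four weeks of self-chosen lifestyle change. The surveillance arm tracks its data only. A favourable view of the programme could then enter the primary endpoint as better quality of life.

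Baseline adjustment does not remove this. The baseline answers are given before participants know their arm, so they cannot refer to the assigned programme. The week-10 answers can. At stake is the interpretation of a positive primary result: part of it could be satisfaction rather than fewer symptoms, better function or less worry.

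**Working it through.** **1. Reproducing the Table 2 range.** The items scored 1 to 7 in Appendix A are:
- four-week items: 4 symptom + 2 limitation + 6 difficulty + 2 worry about AF + 4 worry about treatment = 18;
- present-time satisfaction items: 2.

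The total is 18 + 2 = 20. The lowest sum is 20 × 1 = 20 and the highest is 20 × 7 = 140, which matches Table 2 exactly. Eighteen items would give 18 to 126. The 20-140 range is therefore possible only with both satisfaction items included.

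**2. Weight of the two items.** Each spans 6 points, so together they make up 12 of the 120 points of range, or 10%.

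**3. The plan's sample size.** SAP 5.2 gives a difference of 5, SD 19, 239 per group and 80% power. SAP 5.4.1 gives a significance level of 0.05, taken here as two-sided. The normal approximation n = 2 × (1.96 + 0.84)² × 19² / 5² gives 227 per group, and 239 per group gives about 82% power. The plan's figure is thus slightly conservative for its own inputs. This does not bear on the point, but it fixes the standard error used below: 19 × √(2/239) = 1.74.

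**4. What a shift on the two items alone would do.** The documents give no expected shift, so the shifts below are assumptions. They suppose no difference between arms on the other 18 items. Raw movement is 2 × shift; on a 20-item 0-100 rescaling it is 2 × shift × 100/120. The chance of a significant result is Φ(b/1.74 − 1.96) + Φ(−b/1.74 − 1.96), where b is the movement. No precision gain from covariance adjustment is assumed. Each pair of columns takes the 5-point target and SD 19 to be on that column's scale.

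| Shift per item | Raw points (share of 5) | Chance of significance | 0-100 points (share of 5) | Chance of significance |
|---|---|---|---|---|
| Half a category | 1.0 (20%) | 8.9% | 0.83 (17%) | 7.7% |
| One category | 2.0 (40%) | 21% | 1.67 (33%) | 16% |

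With no shift the chance is 5%.

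**5. Direction and scale.** In Appendix A, 1 is the best answer and 7 the worst on every item, so improvement lowers a raw 20-140 sum. SAP 5.2 quotes 58 ± 19 and speaks of therapies improving the score by 5 to 10. It states neither direction nor range. The documents therefore do not settle which column of the table applies, or whether either does.

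**The case against.** **The scoring rule may not be final.** Table 2 lists data to be collected, and the entry could be read as a data range rather than an algorithm. The sample-size text cites the instrument's validation study and may rest on another scoring. This stands in part: direction and scale do need settling. But Table 2 is the only definition in the plan, and it needs all 20 items.

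**The items do not name the programme.** The block just before them mentions medications, procedures and blood thinners, so many participants will answer about those. Participants in either arm may be on such treatment. SAP 4.5 does call N-of-1 and usual care treatments, but that is analysts' language and not survey wording. This stands: an arm-specific reading is plausible for some participants and is not shown for all. The week-10 survey also follows a four-week lifestyle period in which trigger reminders have stopped, so the rating may concern the changes made rather than the testing itself.

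**The cut is incomplete.** Four treatment-worry items stay among the 18, and all 20 items are unblinded self-report. This also stands. What sets the two items apart is a different construct and a different time frame, together with a direct request to rate treatment.

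**Satisfaction may be a real benefit.** Satisfaction with control and relief lies close to the trial's aim of controlling symptoms. That is a reason to report it visibly, which a separate score does.

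A reader might go further and infer that a positive result would be an artefact, or that 40% of the target effect is bias. The documents support neither. They give no shift, and the 40% also needs the 5-point target to be in raw points.

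**Conclusion.** The point holds as a matter of score definition. The 20-140 total necessarily includes two present-time treatment-satisfaction items in an endpoint labelled quality of life. Because arm is revealed after the baseline survey, those items can take on an arm-related meaning at week 10 that baseline adjustment cannot remove.

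The size is unknown. An assumed shift of half to one category on both items, with nothing else changed, gives 1 to 2 raw points, or 0.83 to 1.67 on the rescaling: 17% to 40% of the 5-point target, depending on its scale. These figures illustrate what is possible and do not estimate bias. Nor would removing the two items make the endpoint free of open-label influence, since the other 18 are also self-reported with knowledge of arm. The change is worth making before analysis because it affects what the primary result means and costs little.

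**What to change.** - In SAP Table 2 and SAP 4.2, define the primary AFEQT score from the 18 four-week items, confirmed against the scoring rules of the cited instrument.
- Report the two satisfaction items as a separate secondary score and the 20-item total as a sensitivity analysis, with the same scoring at baseline and week 10.
- State the score's direction and range. In SAP 5.2 and Protocol 1.7.1, confirm that 58 ± 19 and the 5-point target are on that same scale.

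The cost is SAP wording and scoring code; every item is still collected. There are two downsides. The 18-item effect may be slightly smaller if satisfaction is part of the benefit. The target and SD must also be confirmed for the chosen score: the documents give no SD for an 18-item version, so the sample size cannot be recomputed from them.
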